Statistical analysis plan:

Impact of Repeated Antioxidant Supplementation of Embryo Culture Media on Blastocyst Utilization and Expansion Rate Under Two Different O₂ Concentrations

October 31st, 2021

Research Questions:

- What is the effect of antioxidant supplementation and O2 tension on blastocyst utilization rate and blastocyst expansion rate in infertile women?
- Are there any significant differences in the outcomes between the different antioxidant supplementation protocols and O2 tensions?

Statistical Tests:**Sample Size:**

The total number of blastocysts analyzed was 1797, obtained from 3603 zygotes and 4924 inseminated oocytes. The study included 293 infertile women with a mean age of 32.2 ± 3.3 years.

Data Handling:

For statistical analysis, the data collected consisted of the continuous variable of age, which was expressed as the mean \pm standard deviation in each study group. In addition, the frequency and percentage of usable and expanded blastocysts were recorded as categorical variables.

Comparisons between treatments were performed by calculating the odds ratio and the chi-square test. A significance level of $p < 0.05$ was established to determine the existence of statistically significant differences between groups.

Confounding Variables:

Other treatments or medications: Although there is no explicit mention of other treatments or medications received by the participants in addition to antioxidant supplementation, it is essential to acknowledge that there may be confounding variables present. It is possible that other interventions or medications used in the management of infertility could interact with antioxidant supplementation and potentially influence the study outcomes.

Sensitivity analysis:

The odds ratio analysis with a confidence interval of 95%

9. Statistical Software:

R Core Team was employed for statistical analysis.

10. Data Interpretation:

The results were interpreted by analyzing and comparing the blastocyst utilization rates, blastocyst expansion rates, and cumulative blastocyst utilization and expansion rates across the four study

groups. Statistical analyses, such as odds ratios (OR) and chi-square tests, were used to determine the significance of the differences observed. The level of significance was set at $p < 0.05$.

The findings indicated that antioxidant supplementation had a positive impact on the development and usability of blastocysts. The groups receiving antioxidant supplementation every 12 hours (groups 1A and 2A) consistently showed higher blastocyst utilization and expansion rates compared to the groups with antioxidant supplementation only at the beginning of embryo culture (groups 1B and 2B). These results suggest that regular and sustained antioxidant exposure during embryo development may enhance the overall quality and viability of blastocysts.

Additionally, subgroup analyses were conducted based on the O₂ tension (20% vs. 5%) and the timing of antioxidant supplementation (every 12 hours vs. baseline only). These subgroup analyses allowed for a more detailed understanding of the effects of different conditions on blastocyst outcomes. The subgroup analyses consistently demonstrated that the groups with regular antioxidant supplementation every 12 hours (groups 1A and 2A) had superior blastocyst utilization and expansion rates compared to the groups with baseline-only supplementation (groups 1B and 2B).

In terms of clinical or practical significance, the findings suggest that incorporating antioxidant supplementation, particularly with a frequent administration schedule, can improve the development, expansion, and overall utilization of blastocysts in assisted reproductive technologies. This may have important implications for infertility treatments, as higher blastocyst quality and viability are associated with increased chances of successful embryo transfer and higher pregnancy rates. By optimizing embryo culture conditions through antioxidant supplementation, clinicians and embryologists can potentially improve clinical outcomes and increase the success rates of infertility treatments, offering hope to couples struggling with fertility issues.

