Therefore, it is conceivable that even minimal handling of gamete and embryos could induce OS. This assumption highlights the demand for strategies aiming to reduce the detrimental effects of OS. Implementation of AOX supplementation could help protect against OS damage attributed to alterations in laboratory conditions in the IVF setup. Antioxidants act as a counterpart of ROS, inhibiting their overproduction or neutralizing them when provided in sufficient concentrations (Agarwal et al., 2005; Carocho & Ferreira, 2013). The role of AOXs in enhancing the embryo's potential to successfully reach the blastocyst stage has been demonstrated (Guerin, 2001; Budani & Tiboni, 2020). The blastocyst quality of the expansion grade has been analyzed by the measurement of the blastocoel and has been associated with increased ongoing pregnancy rates (David Gardner et al., 1999)

Considering the pivotal role of AOXs *in vivo*, their implementation in embryo cultures *in vitro* is thought to help mimic the human reproductive tract's natural conditions. Previous studies have investigated the role of non-enzymatic AOX molecules namely vitamin C, vitamin E, selenium, zinc, taurine, hypotaurine, glutathione, and carotene on embryo culture (Agarwal et al., 2005; Carocho & Ferreira, 2013).

Previously, our group determined the oxidation-reduction potential (ORP) values of follicular fluid in oocyte donors and established them as the "physiological" desirable ORP in embryo culture media to maintain a redox state during the entire embryo culture similar to what is observed *in vivo* (Truong, T., & Gardner, D.K., 2017)

However, the current literature is lacking studies to develop a physiological *in vitro* AOXs system that can effectively mitigate the OS phenomenon.

The present study aims to explore whether repeated supplementation of the embryo culture medium with AOXs every 12 hours to culture embryos in ORP physiological levels, could improve the cumulative rates of usable and expanded blastocysts of human embryos from infertile patients as assessed at two different O₂ concentrations (5% and 20% O₂) on days 5 and 6.

Research Design:

Study type: Interventional

Study Model: Parallel Assignment

Participants: 293 Infertile women aged 18 to 37 years at the time of oocyte collection, with tubal factor, polycystic ovary syndrome, uterine factor, or unexplained infertility.

Allocation

Zygotes will be randomly assigned to one of four groups.

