- Group 1A: Antioxidants will be administered every 12 hours at 5% O₂ tension.
- Group 1B: Antioxidants will be administered every 12 hours at 20% O₂ tension.
- Group 2A: Antioxidants will be administered once at the beginning of embryo culture at 5% O₂ tension.
- Group 2B: Antioxidants will be administered once at the beginning of embryo culture at 5% O₂ tension.

Methods:

Study Location and Duration:

The study will be conducted at the Center for Technological Innovation and Reproductive Medicine (CITMER), Mexico City, Mexico, from October 2021 to May 2022.

Participants:

Eligible participants will include infertile women with tubal factor, polycystic ovary syndrome, uterine factor, and unexplained infertility, who have had fertilization of more than 2 oocytes by conventional in vitro fertilization (cIVF) and intracytoplasmic sperm injection (ICSI).

Exclusion criteria will involve low ovarian response patients (fewer than 6 oocytes obtained after oocyte retrieval) and patients older than 37 years.

Sample Size and Group Allocation:

A total of 3603 zygotes obtained from 293 patients will be included in the study.

The zygotes will be divided into four groups based on the following conditions:

Group 1A: Antioxidants will be administered every 12 hours at 20% O₂ tension (793 zygotes).

Group 1B: Antioxidants will be administered only at the beginning of embryo culture at 20% O₂ tension (1286 zygotes).

Group 2A: Antioxidants will be administered every 12 hours at 5% O₂ tension (695 zygotes).

Group 2B: Antioxidants will be administered only at the beginning of embryo culture at (829 zygotes).

The procedures followed for IVF/ICSI involved the following steps:**Ovarian stimulation:**

Different ovarian stimulation protocols were used, including the gonadotropin-releasing hormone (GnRH) antagonist protocol with Cetrotide®, in combination with rFSH and rLH in Pergoveris®.

GnRH antagonist protocols were also used with follitropin alfa in Gonal-F® or with human menopausal gonadotropin in Merapur®

Gamete Retrieval:

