Timeline and Frequency of Assessments:

Data collection will be performed at specific time points, specifically on day 5 and day 6 of the study.

Outcome Measures:

- Usable blastocysts on day 5.
- Expanded blastocysts on day 5.
- Usable blastocysts on day 6.
- Expanded blastocysts on day 6.
- Cumulative usable blastocysts.
- Cumulative expanded blastocysts.

Ethical Considerations:

The study was conducted in accordance with the Declaration of Helsinki and approved by the Institutional Ethics Committee of CITMER CE-20-102.

Data analysis

The statistical analysis of the data will be performed using the R statistical software by the R Core Team.

Statistical Methods:

For statistical analysis, the data collected consisted of the continuous variable of age, which was expressed as the mean \pm standard deviation in each study group. In addition, the frequency and percentage of usable and expanded blastocysts were recorded as categorical variables.

Comparisons between usable and expanded blastocysts from each treatment were performed by calculating the odds ratio and chi-square test. A significance level of $p < 0.05$ was established to determine the existence of statistically significant differences between groups.

References.

1. Khalied Kaskar, C. Optimizing embryo culture conditions and spent culture media analysis as predictors of embryo quality and pregnancy; PhD Thesis, University of the West Cape, Cape Town, South Africa, February 2021.
2. Swain, J.E. Optimizing the culture Environment in the IVF Laboratory: Impact of PH and Buffer Capacity on Gamete and Embryo Quality. *Reprod Biomed Online* **2010**, *21*, 6–16.
4. Nastri, C.O.; Nóbrega, B.N.; Teixeira, D.M.; Amorim, J.; Diniz, L.M.M.; Barbosa, M.W.P.; Giorgi, V.S.I.; Pileggi, V.N.; Martins, W.P. Low versus Atmospheric Oxygen Tension for Embryo Culture in

Assisted Reproduction: A Systematic Review and Meta-Analysis. *Fertil Steril* **2016**, *106*, 95-104.e17, doi:10.1016/j.fertnstert.2016.02.037.

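### The SAP already reports results and sets no primary outcome, contrast list or multiplicity rule for six outcomes in four groups, so its unadjusted 5% level is not the overall error rate (about 5–19% for the stated aim, more for wider readings)

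*SAP*

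**What the plan says.** **Outcomes.** The protocol's Outcome Measures section has six entries, starting with "Usable blastocysts on day 5": usable and expanded blastocysts, each on day 5, on day 6 and cumulatively. None is called primary. The nearest thing to a ranking is the aim at the end of the Introduction, which asks whether 12-hourly supplementation "could improve the cumulative rates of usable and expanded blastocysts of human embryos from infertile patients" at two O₂ settings.

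**Tests.** Statistical Methods (protocol) and Data Handling (SAP) both use odds ratios and chi-square tests. In the SAP the p<0.05 level "was established to determine the existence of statistically significant differences between groups". Neither document lists contrasts, sets a testing order or mentions adjustment. The SAP's Research Questions cover both supplementation and O₂. Its Data Interpretation section sets 1A and 2A against 1B and 2B and mentions subgroup analyses by O₂ and by timing, without saying how many. Its Sensitivity analysis section plans odds ratios with 95% confidence intervals.

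**Dates.** The SAP is dated October 31st, 2021. The protocol places the study "from October 2021 to May 2022". The SAP nevertheless reports 1797 blastocysts from 3603 zygotes and 4924 inseminated oocytes, a mean age, and conclusions. The protocol's planned totals, 3603 zygotes and 293 patients, equal the SAP's final totals.

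**Group labels.** Under Allocation: "Group 1B: Antioxidants will be administered every 12 hours at 20" percent O₂. Under Sample Size and Group Allocation: "Group 1B: Antioxidants will be administered only at the beginning of embryo culture at 20" percent O₂. The two lists conflict.

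**The concern.** A 5% level applies to one test. With six outcomes, four groups and no list of contrasts, the plan permits anything from two tests to several dozen. The chance of at least one false significant result depends on a number that the plan leaves open.

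A prespecified SAP would normally fix that number. This one was completed with results in hand, so it cannot limit which outcomes and contrasts were selected. A single p<0.05 from this set is weaker evidence than the stated level suggests. The Data Interpretation section gives no odds ratio, confidence interval, p-value or test count, so a reader cannot tell which comparisons its conclusion covers.

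**Working it through.** The documents state no familywise error rate, power or sample-size derivation, so there is no plan figure to reproduce.

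**Inputs from the documents.** Group sizes are 793, 1286, 695 and 829 zygotes, and 793 + 1286 + 695 + 829 = 3603, as stated. Conditions follow the protocol's sample-size list. That list omits the O₂ value for the fourth group; 5% is assumed for this calculation only. Pooled by timing: 793 + 695 = 1488 (12-hourly) versus 1286 + 829 = 2115 (once). Blastocyst share: 1797/3603 = 0.499. Level: 0.05 per test.

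**Assumed, because the documents do not give them.** Day-5 share of blastocysts 0.50–0.98; usable share 0.6–1.0; expanded share 0.5–1.0 among usable and 0–0.5 among non-usable blastocysts; expansion rate per zygote or per blastocyst; zygotes independent.

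**Number of tests.**
- Timing within each O₂ setting: 2 contrasts × 6 outcomes = 12.
- Adding O₂ within each timing: 4 × 6 = 24.
- All pairs: (4 × 3/2) × 6 = 36.

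**Formulas.** For k independent tests the familywise rate is 1 − 0.95^k. This overstates the rate for the larger families, because the cumulative outcomes combine day 5 and day 6 and the contrasts share groups. The rate was therefore simulated: multinomial counts under no effect, 116 scenarios of 20,000 runs, X² = Σ(x_g − n_g·p)² / (n_g·p·(1 − p)) with p the pooled proportion, counting runs with at least one p<0.05.

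| Family | Tests | 1 − 0.95^k | Simulated | With continuity correction |
|---|---|---|---|---|
| Two cumulative rates, pooled timing | 2 | 9.8% | 4.7–10.1% | 4.3–9.1% |
| Two cumulative rates, timing within O₂ | 4 | 18.5% | 9.3–19.3% | 8.2–16.9% |
| Six outcomes, pooled timing | 6 | 26.5% | 10.1–22.7% | 7.8–20.2% |
| Six outcomes, one four-group test each | 6 | 26.5% | 10.0–23.3% | not computed |
| Six outcomes, timing within O₂ | 12 | 46.0% | 19.0–40.1% | 13.6–34.9% |
| As above plus O₂ contrasts | 24 | 70.8% | 29.8–57.4% | 22.0–51.8% |
| All pairs | 36 | 84.2% | 37.1–66.4% | 27.7–60.6% |

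A second simulation with six other assumed sets of shares (40,000 runs each) gave 13.6–22.1% for 6 tests, 25.5–38.0% for 12, 39.2–55.3% for 24 and 46.5–63.8% for 36, all inside these ranges.

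**After the fix.** Holm on the four cumulative tests compares the ordered p-values with 0.05/4 = 0.0125, 0.05/3 = 0.0167, 0.05/2 = 0.025 and 0.05. Under no effect the simulated familywise rate is 2.2–5.3% (1.9–4.4% with continuity correction). The 5.3% is within simulation error of 5%.

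**The case against.** **The aim already narrows the question.** It names 12-hourly supplementation, two cumulative rates and two O₂ settings. On that reading the error is 5–10% or 9–19%, and the lower end is the nominal level. This stands as far as it goes, and those figures should come first. But the aim does not call either rate primary, and the outcome list, the research question on O₂ and the subgroup analyses all go beyond it.

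**The SAP claims a uniform pattern, not one significant result among many.** In one assumed null scenario, all 12 within-O₂ comparisons favoured 12-hourly supplementation in only about 1.5–2% of runs, and all four cumulative tests were significant in that direction in under 0.3%. A reader might infer from the familywise rates that the SAP's conclusion is wrong. The documents do not support that. Nor do they support the conclusion fully, because the SAP does not say which comparisons it covers, and overlapping outcomes do not confirm one another independently.

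**The largest figure has little textual basis.** A reader might take the all-pairs 37–66% as the trial's error rate. It requires diagonal contrasts, such as 12-hourly at 20% O₂ against once at 5% O₂, and neither document names one. It is an upper bound only.

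**Dating.** A reader might infer deliberate backdating. The documents show only that the present text cannot all have been written on the stated date. Results may have been added to a plan that was dated correctly.

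**Holm applied after the data are known does not restore prespecification.** This is true; the gain is disclosure and a more cautious threshold.

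**Conclusion.** The point holds in this limited form. As it stands, the SAP is a mix of plan and results and cannot show that the analyses were chosen in advance. The testing rule exceeds a 5% overall error on every reading except the lower end of the narrowest one.

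The exact size is uncertain. It rests on outcome shares that the documents do not give, on uncorrected chi-square tests and on independent zygotes. The finding that outcomes are unranked, contrasts unlisted and results already present rests on the text alone and needs no simulation.

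Clustering by patient is a separate matter. The protocol says "Zygotes will be randomly assigned to one of four groups", while age is to be summarised with its "standard deviation in each study group", so the allocation unit is not clear. No clustering is built into the figures here.

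**What to change.** 1. State the true date of the SAP and whether a dated plan predating the results exists. Move the conclusions in Data Interpretation and the realised counts under Sample Size to the report.
2. In the report, state how many tests were run. Take as the main family the two cumulative rates, 12-hourly versus once within each O₂ setting: four tests with Holm-adjusted p-values.
3. Define those tests by condition, not by label, because the two group lists in the protocol conflict and must be reconciled.
4. Disclose that the family was chosen after the data were seen, follows the protocol's aim and is not confirmatory. It puts supplementation ahead of O₂, although the SAP asks about both, so this choice should be explicit.
5. Report the O₂ contrasts and the day 5 and day 6 outcomes with the odds ratios and 95% confidence intervals the SAP already plans, without significance claims. Word the report's conclusions to match.
6. State the allocation unit. If whole patients went to one group, the four p-values must allow for clustering by patient before Holm is applied.

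**Cost.** Changes to SAP and report wording, a count of the tests and an adjustment of four p-values, with no new data. A clustered model is extra work if step 6 requires it. The downside is fewer results called significant and a weaker claim.

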Oocyte retrieval will be performed 36 hours after the administration of choriogonadotropin alfa (Ovidrell®, Merck Serono, Bari, Italy). Cumulus-oocyte complexes (COCs) will be transferred into dishes containing HTF HEPES® (InVitroCare®) supplemented with 10% human serum albumin (HSA) (InVitroCare®) and antioxidants (EmbryORP®). COCs will then be washed and placed in culture media (global® total®, Life global® Group) with stock antioxidants (EmbryORP®) until insemination.

Fertilization:

For intracytoplasmic sperm injection (ICSI) cases, mature oocytes (metaphase II) will be denuded using Hyaluronidase (10%) (InVitroCare®) approximately 40 hours after HCG administration. Only mature oocytes will be selected and injected. For conventional IVF insemination, oocytes will be co-incubated individually with capacitated sperm in embryo culture media for 17 to 20 hours.

Embryo Culture:

After the fertilization check, zygotes will be cultured under specific conditions in an incubator. The incubator settings will be either 37°C, 8% CO₂, 20% O₂, and 95% relative humidity (RH) or 37°C, 8% CO₂, 5% O₂, and 25% RH. Only 2 pronuclei (PN) zygotes will be considered for the study.

Antioxidant Supplementation:

The antioxidant supplementation protocol will involve the use of EmbryORP®, a novel antioxidant consisting of a mixture of four different compounds: reduced L- cysteine, L- glutathione, L- ascorbic acid, and L- carnitine hydrochloride (0.0124 M for carnitine, 0.0165 M for cysteine, 0.0065 M for glutathione, and 0.0227 M for ascorbic acid). Groups 1A and 2A, 6.5 µL of EmbryORP® antioxidants will be added at the beginning of the culture (in the zygote stage), followed by the addition of 3.5 µL of stock antioxidant media (EmbryORP®) every 12 hours. For groups 1B and 2B, 6.5 µL of EmbryORP® antioxidants will be added only at the beginning of the culture control of O₂ Tensions:

During embryo culture, two different O₂ tensions will be maintained. The first setting will be 20% O₂, and the second setting will be 5% O₂. These O₂ tensions will be controlled using the incubator, which will provide the desired atmospheric conditions.

Data Collection:**Variables to be Measured:**

The blastocyst expansion rate will be assessed by calculating the proportion of blastocysts that reach the expanded stage. Embryo evaluation will be performed based on the Gardner and Schoolcraft criteria from 1999, and the results will be documented in standardized databases.

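### The SAP credits antioxidant supplementation itself with a benefit, but all 3603 zygotes are supplemented, so the trial can compare only repeated with single supplementation

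*SAP*

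**What the plan says.** **Exposure.** Under Gamete Retrieval, the Protocol puts EmbryORP in the medium that receives the cumulus-oocyte complexes, then holds them in culture medium "with stock antioxidants (EmbryORP®) until insemination". Under Antioxidant Supplementation, groups 1A and 2A get 6.5 µL at the zygote stage and 3.5 µL every 12 hours after that. Groups 1B and 2B get the same 6.5 µL at the start and nothing later.

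**Aim.** The Protocol introduction sets out to learn whether repeating the supplementation every 12 hours improves usable and expanded blastocyst rates. The study title also speaks of repeated supplementation.

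**SAP questions.** Question 1 is broader: "What is the effect of antioxidant supplementation and O2 tension on blastocyst utilization rate and blastocyst expansion rate in infertile women". Question 2 asks separately about schedules: "Are there any significant differences in the outcomes between the different antioxidant supplementation protocols and O2 tensions".

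**SAP conclusions.** Section 10 begins: "The findings indicated that antioxidant supplementation had a positive impact on the development and usability of blastocysts". Its next sentence gives the evidence, which is a comparison with groups 1B and 2B: "The groups receiving antioxidant supplementation every 12 hours (groups 1A and 2A) consistently showed higher blastocyst utilization and expansion rates". The last paragraph suggests that "incorporating antioxidant supplementation, particularly with a frequent administration schedule, can improve the development, expansion, and overall utilization of blastocysts", and ends: "By optimizing embryo culture conditions through antioxidant supplementation, clinicians and embryologists can potentially improve clinical outcomes".

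**Incubators.** Under Embryo Culture, the Protocol gives two settings with the same temperature and CO₂. One has 20% O₂ and 95% relative humidity (RH); the other has 5% O₂ and 25% RH. The SAP questions and the subgroup sentence in section 10 name this factor by O₂ tension only.

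**The concern.** A difference between two schedules does not show that either is better than none. The evidence in section 10 is entirely repeated against single, yet its opening sentence and its practical advice attribute the benefit to supplementation as such. In the advice, the frequent schedule appears as a refinement of a general benefit that the trial never tested.

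The wording matters because section 10 presents it as a message for practice. A laboratory that uses no antioxidants could take it as evidence for starting, and the trial has no data on that question.

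The second issue is smaller. SAP questions 1 and 2 ask about O₂ tension, so a reader could take any 20% versus 5% difference as an oxygen effect, although humidity changes with it.

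**Working it through.** **Inputs.** The counts come from the Protocol, Sample Size and Group Allocation. Exposure comes from Antioxidant Supplementation, and the incubator settings from Embryo Culture.

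| Group | Zygotes | At start | Every 12 hours | O₂ / RH |
|---|---|---|---|---|
| 1A | 793 | yes | yes | 20% / 95% |
| 1B | 1286 | yes | no | 20% / 95% |
| 2A | 695 | yes | yes | 5% / 25% |
| 2B | 829 | yes | no | O₂ not stated; 5% / 25% by elimination |

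**1. Stated total.** 793 + 1286 + 695 + 829 = 3603, which matches the Protocol.

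**2. Split by antioxidant exposure.**
- Repeated (1A + 2A): 793 + 695 = 1488; 1488/3603 = 41.3%.
- Single (1B + 2B): 1286 + 829 = 2115; 2115/3603 = 58.7%.
- Unsupplemented: 3603 − 1488 − 2115 = 0.

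**3. Does the conflict between the group lists change this?** The Protocol defines the groups twice. The earlier list, under Allocation, makes 1A and 1B repeated (5% and 20% O₂) and 2A and 2B single (both at 5%). Attaching those labels to the counts gives 793 + 1286 = 2079 repeated and 695 + 829 = 1524 single. The total is again 3603, with none unsupplemented. The zero holds under both lists; the 1488/2115 split does not.

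**4. What can be estimated.** Take a model for the four groups in the table with five columns: intercept, any antioxidant, repeated, O₂ and RH.
- Any antioxidant equals 1 in every group, so it is identical to the intercept. Those two columns have rank 1.
- RH is an exact linear function of O₂: RH = 25 + (70/15) × (O₂ − 5), which gives 25 at 5% and 95 at 20%. Intercept, O₂ and RH together have rank 2.
- All five columns have rank 3. Besides the intercept, the design supports repeated versus single and one combined O₂/RH factor, plus their interaction.

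The planned odds ratio and chi-square test therefore cannot address supplementation versus none, because the unsupplemented row of the table would be empty. A larger sample of the same four groups would not help.

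**5. Incubator contrast.** Two O₂ levels and two RH levels make 4 possible combinations; the Protocol uses 2. With 2B taken as 5% O₂, the settings hold 793 + 1286 = 2079 and 695 + 829 = 1524 zygotes. The documents give neither size nor direction for a humidity effect, so none is estimated.

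**The case against.** The best defence is context. The title and the Protocol aim both say repeated. The sentence straight after the broad opening of section 10 names the right groups, and the paragraph goes on to speak of regular and sustained exposure. The advice on incorporating supplementation is introduced as something that the findings suggest, and the closing sentence says only that outcomes can potentially improve. Question 1 could be read as shorthand for the schedule.

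Much of this stands. The sentences comparing 1A and 2A with 1B and 2B state a contrast that the design allows and need no change on this point. The second and third statements are hedged, and question 1 is ambiguous rather than plainly wrong. But hedging expresses uncertainty about a result, whereas here the comparison is absent. Question 2 already covers the schedules, which makes the broad reading of question 1 a natural one. The opening sentence is not hedged at all.

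It is also fair to say that little rests on the humidity point. Section 10 draws no conclusion about a main effect of O₂, and humidity does not disturb repeated versus single within one incubator setting. A reader might infer that humidity biases the antioxidant result or explains an oxygen result. The documents support neither inference; they show only that the two factors cannot be separated.

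**Conclusion.** The point holds as a correction to wording. None of the 3603 zygotes is unsupplemented, so the unhedged opening of section 10 and its hedged advice on incorporating supplementation claim an effect that the design cannot test. The closing sentence, also hedged, follows the same wording. The zero rests on the Protocol's description of exposure and does not depend on which group list applies. The split of 1488 against 2115 assumes that the A groups are repeated and the B groups single, as in Antioxidant Supplementation and SAP section 10.

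Two stronger readings should be resisted. A reader might infer that the trial cannot answer its own question; but the aim concerns repeated supplementation, and that contrast is present. A reader might also infer that supplementation does not help; the trial has no evidence on that in either direction.

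The humidity point is secondary and conditional. If the stated RH values are right, the O₂ factor is a combined setting; if RH was in fact equal in both incubators, the point lapses.

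**What to change.** 1. In SAP section 10, reword the opening sentence, the statement on incorporating supplementation and the closing sentence on optimizing culture conditions so that each refers to repeated versus single supplementation. State that there was no unsupplemented group.
2. In SAP question 1, narrow only the antioxidant phrase in the same way. Keep the O₂ part.
3. Reconcile the two group lists in the Protocol before describing the contrast as made within each incubator setting. The list under Allocation has no single-supplementation group at 20% O₂, and the list under Sample Size and Group Allocation gives no O₂ value for 2B. The rewording in items 1 and 2 need not wait for this.
4. Ask the sponsor to confirm the two RH values. If they stand, label the factor in SAP questions 1 and 2 and in the section 10 subgroup sentence as the combined O₂/RH setting.

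The cost is a few sentences of SAP text, one query on the RH values, and the reconciliation of the group lists, which is needed in any case. No new data or reanalysis is required for the rewording. The downside is a narrower claim.
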